1 INTRODUCTION

1.1 BACKGROUND

Vascular dysfunction in pregnancy, manifesting as pre-eclampsia, fetal growth restriction, and stillbirth, causes significant morbidity and mortality worldwide for mothers and babies. Pre-eclampsia affects up to 6% of pregnancies and causes 500,00 fetal and 70,000 maternal deaths each year(1). Beyond the immediate impacts, mothers who suffer from pre-eclampsia, and children who were growth restricted in utero, have elevated risks of cardiovascular and metabolic disease throughout their lives(2,3).

National guidelines recommend aspirin prophylaxis commenced prior to 16 weeks' gestation to reduce the risk of pre-eclampsia, fetal growth restriction and stillbirth in women at high risk of placental dysfunction(4). The most effective first trimester risk prediction algorithms incorporate uterine artery Doppler measurements and blood biomarkers like placental growth factor (PIGF) or pregnancy associated plasma protein-A (PAPP-A) assessed at 12 weeks' gestation. Despite an ~82% sensitivity for preterm pre-eclampsia, this screening test is a poor predictor for pre-eclampsia occurring at >37 weeks' gestation, which is the majority of disease(5). Moreover, risk stratification tools based on one-off measurements at a single time point cannot predict likely clinical trajectory of disease or time to deterioration. The lack of robust strategies to guide management presents challenges for clinicians, in implementing appropriate prophylaxis, monitoring and timely delivery, and in minimising harms associated with excessive intervention and iatrogenic birth at unduly early gestations.

Ophthalmic artery Doppler indices show promise as predictive markers for pre-eclampsia, at both early and late gestations(6). Meanwhile, retinal microvascular changes are reported preconception, antenatally, and postpartum in women with pregnancies affected by placental dysfunction(7,8,9,10,11). The eye may therefore represent a "window" into maternal cardiovascular adaptation to pregnancy. Serial retinal vascular imaging of pregnant women longitudinally throughout gestation is being carried out through the *I-TEST* study (REC 332944), with the aim of identifying novel retinal imaging-derived biomarkers as non-invasive measures of maternal vascular responses to pregnancy.

Computational fluid dynamics and machine learning advances are enabling increasingly precise modelling of complex biological systems, including the pregnant maternal circulation. Such models can be personalised with data from pregnant individuals to produce accurate predictions of blood flows and resistances within specific vascular beds, including placental and retinal microcirculations, at greater resolutions than measurable with non-invasive techniques(12,13).

This study will be nested within the *I-TEST* study, which is recruiting patients for retinal vascular imaging at 12 and 36, or 20 and 36 weeks' gestation (cohort 1), and at 36 weeks' gestation only (cohort 2). In *I-TEST-M*, we will carry out additional assessments of *I-TEST* study participants in the form of longitudinal measurements of ophthalmic and uterine artery Doppler indices and cardiovascular metrics. Integrating these measurements with a computational modelling approach will provide insights into adaptation of the wider maternal circulation to pregnancy. It will also allow us to identify novel vascular biomarkers relating to ophthalmic artery and systemic circulatory metrics which can indicate maladaptive maternal vascular responses, and be integrated into models that are predictive of the risk of placental dysfunction.

1.2 RATIONALE FOR STUDY

Our main aim is to identify and test novel biomarkers relating to retinal vascular, ophthalmic artery and systemic circulatory blood flows, for early detection of pregnancy complications and integration into models that are predictive of pre-eclampsia, fetal growth restriction and stillbirth. We will use a computational modelling approach to simulate blood flows within the maternal circulation and investigate the relationship between changes in the retinal and uteroplacental circulations during normal pregnancies and those affected by vascular dysfunction. This approach will complement that

of the *I-TEST* study, which aims to develop retinal imaging-derived biomarkers of placental dysfunction and within which our sub-study is nested, by relating structural retinal vascular changes with physiological adaptation of the entire maternal circulation.

We hypothesise that retinal vascular changes reflect the dynamic remodelling of maternal systemic and uteroplacental circulations during pregnancy. This could provide opportunities to monitor vascular responses to pregnancy non-invasively and in real time, allowing improved risk stratification and early detection of pregnancy complications.

To test this hypothesis and achieve our study aims, we will address the following research questions:

- 1. How do retinal blood flows change throughout gestation during uncomplicated and disordered pregnancies, and how do these changes relate to adaptation with maternal systemic and uteroplacental circulations?
- 2. Do resistance patterns within the retinal microcirculation correlate with quantitative metrics derived from retinal vascular imaging?
- 3. Do retinal blood flows correlate with established markers of placental function and clinical pregnancy outcomes?
- 4. Can integrating metrics relating to retinal vascular, ophthalmic artery or systemic circulatory blood flows into predictive models of pre-eclampsia and fetal growth restriction improve their performance, over and above current clinical tools?

We anticipate that biomarkers derived from computational models of the maternal cardiovascular system, as it evolves dynamically throughout gestation, will have utility for serial assessment of pregnant women to monitor their vascular adaptation to pregnancy. This could enable clinicians to manage pregnancies where vascular dysfunction is suspected with a more nuanced, personalised and timepoint-specific approach.

2 STUDY OBJECTIVES

2.1 OBJECTIVES

2.1.1 Primary Objective

To collect a range of non-invasive cardiovascular and ultrasound Doppler blood flow metrics longitudinally throughout pregnancy, from women enrolled in the *I-TEST* study.

2.1.2 Secondary Objectives

To integrate the cardiovascular and ultrasound Doppler measurements into personalised computational cardiovascular models that capture changes in vascular resistances and compliances, including within retinal and uteroplacental circulations.

To collect serial urine samples for assessment of proteinuria levels (in addition to blood samples at 36 weeks for measurement of biomarkers of placental dysfunction, and data on key maternal and neonatal outcomes, collected as part of the *I-TEST* study). This will allow correlation of maternal cardiovascular changes with markers of renal microvascular dysfunction, established predictive biomarkers for placental dysfunction, and clinically relevant metrics.

2.2 ENDPOINTS

2.2.1 Primary Endpoint

Generation of circulatory models which simulate blood flows and vascular resistances throughout the maternal circulation at serial timepoints throughout gestation.

2.2.2 Secondary Endpoints

Identification of vascular biomarkers from computational models which can discriminate pregnancies affected by placental dysfunction from healthy pregnancies.

Correlation of retinal and ophthalmic artery haemodynamic metrics derived from computational modelling with structural parameters derived from retinal vascular imaging (through comparison with *I-TEST* study results).

Validation of novel vascular biomarkers against established markers of vascular and placental dysfunction, and subsequent integration of vascular biomarkers into models which are predictive of clinical pregnancy outcomes.

3 STUDY DESIGN

This is an observational study, designed to characterise the maternal cardiovascular response to pregnancy for subsequent identification of vascular biomarkers of placental dysfunction which are suitable for integration into predictive models. It is nested within the *I-TEST* study, through which participants will undergo serial multimodal retinal imaging between 9 and 39 weeks' gestation.

We propose additional assessments of *I-TEST* study participants, in two sequential study arms:

- a. women recruited in late pregnancy, comprising those with healthy pregnancies (controls) and those with diagnosed pre-eclampsia or fetal growth restriction (cases), studied at fortnightly intervals until birth (phase one); and
- b. women studied longitudinally at approximately 12, 28 and 36 weeks' gestations, and 6 weeks postnatally (phase two). These will be an unselected pregnant cohort, enriched with those at higher risk of placental dysfunction who will be invited to additional study visits in late pregnancy to coincide with appointments for fetal monitoring as clinically indicated.

4 STUDY POPULATION

4.1 NUMBER OF PARTICIPANTS

Phase one: 20 pregnant women with singleton pregnancy recruited after 34 weeks' gestation, including 10 with uncomplicated pregnancies and 10 with diagnosed pre-eclampsia (as per International Society for the Study of Hypertension in Pregnancy guidelines) or fetal growth restriction (as per Delphi criteria for small for gestational age)(14,15).

Phase two: 100 women with singleton pregnancy, recruited after antenatal booking and prior to 15 weeks' gestation.

This will be a single site study, involving only participants with pregnancies booked within NHS Lothian.

4.2 INCLUSION CRITERIA

Enrolled in I-TEST

Age 16-50 years

Able to give informed consent

Singleton non-anomalous viable pregnancy

Living in Lothian area

4.3 EXCLUSION CRITERIA

Women who are not pregnant

Aged under 16 or over 50 years

Women who are classified as Adults with Incapacity (AWI) as determined by midwife, GP or research team

Delivery indicated prior to 34 weeks (for phase one)

Multiple pregnancy

Diagnosed congenital anomaly

4.4 CO-ENROLMENT

We will recruit participants from those already enrolled in the *I-TEST* study. To reduce the potential burden on participants, we will aim to align *I-TEST* retinal imaging scans with *I-TEST-M* study visits.

Women will also be able to enrol in additional studies if they choose to do so.

5 PARTICIPANT SELECTION AND ENROLMENT

5.1 IDENTIFYING PARTICIPANTS

All participants recruited to the *I-TEST* study will be screened for eligibility by a member of the research team, and if eligible will be invited to enrol in *I-TEST-M*. Initial contact with potential participants will be by telephone call, email, or in person during attendance at routine antenatal clinics or I-TEST study visits.

5.2 CONSENTING PARTICIPANTS

All procedures will be explained to each participant either by a member of the research team, or by a video on the website, and written information will be provided on a detailed PIS. Prior to providing written consent, all participants will be given ample time to consider whether or not they would like to take part and to ask questions relating to the research. Additionally, it will be made clear both verbally and in writing that all volunteers have the right to withdraw at any time, without giving any reason, this will not affect the care they receive. Informed consent will be sought from the participant themselves as only healthy adults will be recruited. Consent may be given online – via QR code which takes to study website which then links to REDCap database where consent form is contained – or via paper on the day of the study visit.

5.2.1 Withdrawal of Study Participants

Participants are free to withdraw from the study at any point or a participant can be withdrawn by the Investigator or research midwives. If withdrawal occurs, the primary reason for withdrawal will be documented in the participant's case report form, if possible. The participant will have the option of withdrawal from:

- all aspects of the study but continued use of data and samples collected up to that point.
 To safeguard rights, the minimum personally-identifiable information possible will be collected.
- (ii) all aspects of the study but continued use of data and samples collected up to that point and also routine data collection at birth from the electronic health care record. To safeguard rights, the minimum personally-identifiable information possible will be collected
- (iii) all aspects of the study, including withdrawal of all data and samples collected up to the point and withdrawal from any further collection of data or samples.

Women will be able to withdraw from the study at any time by emailing or telephoning a member of the research team, whose contact details will be provided on patient facing materials, or via the website.

6 STUDY ASSESSMENTS

6.1 STUDY ASSESSMENTS

All study visits will take place at the Royal Infirmary of Edinburgh. Where possible, visits will be undertaken to coincide with a routine clinical visit, or with a *I-TEST* study visit for retinal imaging.

The following datasets will be collected at study visits (in addition to data gathered through the *I-TEST* study). In phase one, these will be at fortnightly intervals (±5 days), starting after 34 weeks gestation and continuing until birth. In phase two, these will be at 12, 28 and 36 weeks' gestation and 6 weeks postnatally (±3 weeks for each timepoint), with additional (up to fortnightly) study visits offered for women with diagnosed pre-eclampsia or fetal growth restriction, if these can be aligned with scheduled clinical appointments.

Maternal physiological data:

· Maternal height and weight will be measured.

Maternal cardiovascular data:

- Heart rate and systolic and diastolic blood pressure will be measured lying, sitting and standing.
- Echocardiography or electrocardiography (ECG) cardio-impedance will be conducted for measurement of cardiac output ± aortic size.
- Pulse wave velocity: aortic central pulse wave velocity will be assessed with a tonometry-based device placed sequentially over the carotid and femoral artery in conjunction with simultaneous ECG recording. Peripheral pulse wave velocity will then be assessed with a tonometry-based device placed sequentially over either the carotid and radial arteries, or femoral and popliteal/tibial arteries, in conjunction with simultaneous ECG recording. The distance between points of pulse wave detection will be measured manually to allow calculation of central and peripheral pulse wave velocities. The measurement of pulse wave velocities, both centrally and peripherally, will be repeated three times, or until at least two measures are within 0.5m/s.

Ultrasound assessment:

- Maternal uterine artery Doppler measurements will be made and the pulsatility index from both uterine arteries will be recorded (this assessment is already carried out on all *I-TEST* participants at the 36 week visit *I-TEST-M* would involve further repeated measurements at all study visits).
- Maternal ophthalmic artery Doppler measurements will be made, with waveforms obtained in sequence from the right eye, left eye, and again right and then left eye. The following four indices will be recorded: first peak systolic velocity, second peak systolic velocity, pulsatility index, and ratio of second to first peak systolic velocities (this assessment is already carried out on all *I-TEST* participants at the 36 week visit – *I-TEST-M* would involve further repeated measurements at all study visits).
- Maternal middle cerebral artery Doppler measurements will be made and the pulsatility index from both middle cerebral arteries will be recorded.
- For study visits after 25 weeks' gestation, umbilical artery and fetal middle cerebral artery
 Doppler measurements will be made and the pulsatility index of each recorded, along with the
 cerebroplacental ratio (calculated as the ratio of umbilical artery pulsatility index to fetal
 middle cerebral artery pulsatility index).

Biological samples:

[figure not shown]
 At each study visit during phase two, we will collect a urine sample for analysis of proteinuria (albumin-creatinine ratio) and for processing and storage in the Edinburgh Reproductive Tissue Biobank, allowing for future measurement of other potential biomarkers for placental or vascular dysfunction.

In addition to the serial retinal imaging carried out by I-TEST, participants recruited to phase two of I-TEST-M will undergo additional retinal imaging (scanning laser ophthalmoscopy, optical coherence tomography, and optical coherence tomography angiography) at the 6-week postnatal study visit.

[figure not shown]
Figure 1 demonstrates the schedule of visits in both phases of the study.

Figure 1: study visit schedule

Phase one: case-control study

Phase two: longitudinal cohort study (timings of study visits all +/- 3 weeks)

Additional optional fortnightly study visits. comprising cardiovascular assessment, ultrasound assessment, and repeat urine samples, for participants diagnosed with pre-eclampsia or fetal growth restriction (from diagnosis until birth)

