9.2 PROPOSED ANALYSES

Participant height and detailed cardiovascular and Doppler ultrasound data collected at study visits will be used to personalise patient-specific cardiovascular models, using a two-tier parameter estimation algorithm within a closed-loop 1D-0D circulatory model of pregnancy as described in Carson et al(13). We will extract outputs from these models including predicted measures of aortic diameter and elasticity, and retinal and placental vascular bed resistances.

We will apply correlation analysis to phase one data, to assess relationships between ophthalmic artery Doppler indices and model-predicted aortic and retinal vascular metrics. This will establish whether individual Doppler indices reflect upstream or downstream vascular properties. We will also assess correlation between ophthalmic artery and uterine artery Doppler indices which might suggest synergy between retinal and uteroplacental circulations. Descriptive statistics will be used to compare measures of ophthalmic artery blood flow and retinal vascular resistances between cases and controls, identifying possible candidate biomarkers.

In phase two, we will use a linear mixed effects regression approach to assess longitudinal changes in vascular metrics within individuals, and identify differences in metric trajectories for pregnancies affected by placental dysfunction. We will validate candidate biomarkers of vascular and placental dysfunction by testing associations with proteinuria and 36-week PIGF levels (from blood samples collected as part of the *I-TEST* study), using linear models adjusted for common co-variates, adjusting for multiple comparisons. Separate subgroup analysis will be performed for participants on antihypertensive treatment.

We will assess the relationship between estimates of retinal vascular resistances generated from computational modelling and structural parameters derived from retinal vascular imaging in the *I-TEST study*, using data from phases one and two. This will be through analysis of correlation between model-prediction retinal vascular resistance and metrics derived at the same gestation from retinal imaging, for individual participants.

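### Sections 3 and 6.1 disagree on who gets extra phase-two visits, and section 9.2 does not separate measurements before and after diagnosis, so established disease could be read as early prediction

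*Protocol*

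**What the plan says.** Protocol section 6.1 fixes the phase-two schedule: "these will be at 12, 28 and 36 weeks' gestation and 6 weeks postnatally (±3 weeks for each timepoint". It adds visits "with additional (up to fortnightly) study visits offered for women with diagnosed pre-eclampsia or fetal growth restriction", provided these fit clinical appointments. Figure 1 in the same section describes the extra visits as optional and "for participants diagnosed with pre-eclampsia or fetal growth restriction (from diagnosis until birth".

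Section 3 describes a different group. It calls phase two an unselected cohort "enriched with those at higher risk of placental dysfunction who will be invited to additional study visits in late pregnancy", timed to fetal monitoring appointments. Being at higher risk is not the same as being diagnosed.

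Section 9.2 states that "we will use a linear mixed effects regression approach to assess longitudinal changes in vascular metrics within individuals", and that this will "identify differences in metric trajectories for pregnancies affected by placental dysfunction". It then describes prediction models: linear regression for continuous outcomes, logistic regression for complications, and k-fold cross validation. No prediction time is given, and neither analysis distinguishes measurements made before diagnosis from those made after it. The one related provision is: "Separate subgroup analysis will be performed for participants on antihypertensive treatment".

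Section 1.2 gives the main aim as biomarkers for early detection and for models that predict pre-eclampsia, fetal growth restriction and stillbirth.

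**The concern.** Two things interact.

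First, the protocol does not settle who contributes extra data. Under section 3, some women at risk but without disease would supply extra late measurements. Under section 6.1 and Figure 1, only diagnosed women would. These are different data sets, and the choice between them cannot be made at the analysis stage because it concerns which visits were offered.

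Second, under section 6.1 the outcome itself determines how often a woman is measured, and every extra measurement comes after diagnosis. If these values enter a comparison of affected with unaffected trajectories, a change that begins at diagnosis can tilt the fitted line for affected women across the whole of gestation. If they enter a prediction model, the model is partly recognising disease that has already been diagnosed. Cross validation would not reveal this, because training and test folds contain the same kind of post-diagnosis values.

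At stake are the secondary endpoints on discrimination and prediction (section 2.2.2) and the comparison with routine clinical baselines in section 9.2. The effect sizes to be calculated after the first 50 women (section 9.1) could carry the same distortion. The primary endpoint, generating the circulatory models, is not affected.

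**Working it through.** **Does the protocol give a figure to reproduce?** Not on this point. Section 9.1 says that no effect sizes are available for phase two, and gives no case share or variance. Its one derived figure, 115 recruited for 100 assessed, implies a loss of 1 − 100/115 = 13% and does not bear on this question. The check is therefore a simulation, and its inputs are partly assumptions.

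**From the protocol:** 100 women; antenatal visits at about 12, 28 and 36 weeks; fortnightly extra visits for cases from diagnosis to birth.

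**Assumed:** case share 10%, 20% or 30%; diagnosis at 26-37 weeks; birth 2-5 weeks later; between-woman SD = residual SD = 1, so the intraclass correlation is 1/(1 + 1) = 0.5; every extra visit attended.

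**Model.** Metric = woman effect + shift × (case, at or after diagnosis) + residual, with no difference between cases and other women before diagnosis. The shift is 0, 0.5 or 1 residual SD. In total-SD units the last two are 0.5/√2 = 0.35 and 1/√2 = 0.71. The fit is a random-intercept model with known variance components and a case-by-time term, tested two-sided at 5%, with 300 runs per setting. At a true rate of 5% the simulation standard error is √(0.05 × 0.95/300) = 1.3 percentage points.

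**Share of runs with a significant case-by-time term** (case share 10% / 20% / 30%):

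| Shift after diagnosis | All visits | Scheduled visits only | Pre-diagnosis visits only |
|---|---|---|---|
| 0 | 5.0 / 5.3 / 5.0% | 4.0 / 6.7 / 4.3% | 3.0 / 5.7 / 5.7% |
| 0.5 SD | 21.0 / 37.3 / 43.3% | 6.7 / 12.3 / 14.3% | 3.0 / 5.7 / 5.7% |
| 1 SD | 71.3 / 91.3 / 95.7% | 18.7 / 24.7 / 43.3% | 3.0 / 5.7 / 5.7% |

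- **Measurement imbalance.** Cases average 4.69 antenatal visits against 2.97 in other women, a ratio of 4.69/2.97 = 1.6. Of the case visits, 59% follow diagnosis, or 0.59 × 4.69 = 2.8 per case.
- **Apparent early difference.** With all visits, the fitted case difference at 28 weeks is 0.29-0.34 SD for the 0.5 SD shift and 0.60-0.65 SD for the 1 SD shift. If diagnoses are spread evenly over 26-37 weeks, only (28 − 26)/(37 − 26) = 18% of cases are diagnosed by then, so the real average difference would be about 0.09 and 0.18 SD.
- **Discrimination.** The AUC of a woman's mean metric over all visits is 0.57-0.58 (0.5 SD) and 0.64-0.65 (1 SD). With pre-diagnosis visits, or the 12-week value alone, it is 0.50.
- **Scheduled visits share the problem.** The ±3-week windows put the 28-week visit at 25-31 weeks and the 36-week visit at 33-39 weeks, so either can follow diagnosis. That is why the scheduled-only column also rises.
- **Sensitivity (20% cases, 1 SD).** Diagnosis at 34-38 weeks with birth 0.5-2 weeks later gives 60% with all visits, 8% with scheduled visits and 4% with pre-diagnosis visits. Diagnosis at 26-34 weeks with birth 4-10 weeks later gives 94%, 60% and 6%.

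**The case against.** The strongest reply is that only the protocol is at hand. Landmark times and the handling of post-diagnosis visits are model details that an analysis plan may well settle, and section 9.2 never says that the extra visits enter undifferentiated. Much of this stands: the missing cut-off is not in itself an error. The outcome-dependent schedule and the disagreement over who is offered it, however, are fixed in the protocol.

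Second, early prediction is not the only aim. Section 1.2 asks how flows change in disordered pregnancies, and section 2.2.2 seeks markers that separate affected from healthy pregnancies. For those purposes a divergence after diagnosis is a true difference. This stands fully. The visits are worth having, and the rates above are false positives only for a claim about what preceded diagnosis.

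Third, the antihypertensive subgroup addresses treated disease in part. A reader might infer that it is of no use because treatment follows diagnosis and leaves few unaffected women to compare with. The protocol says neither thing, and enrichment for higher risk could bring in treated women without either diagnosis. What remains is that the subgroup is defined by treatment rather than by date of diagnosis, so it does not cover untreated disease or fetal growth restriction without hypertension.

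Fourth, the extra visits are offered, optional and dependent on clinical appointments, so full attendance is an upper bound. This stands. The scheduled-only column shows the other end, with no uptake at all.

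**Conclusion.** The point holds as a cheap improvement together with a contradiction to reconcile. Sections 3 and 6.1 (with Figure 1) name different groups for the extra visits. Under section 6.1, pooling all measurements could make established disease look like an early difference: about 21-43% of runs at a 0.5 SD shift and 71-96% at 1 SD, against 3-6% when only pre-diagnosis visits are used.

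These figures are illustrative. They rest on an assumed case share, diagnosis time, interval to birth, variance split, shift and full attendance. Section 1.1 says that most pre-eclampsia occurs after 37 weeks, later than the main scenarios assume; later diagnosis with early birth lowers the rate (60% instead of 91% at 20% cases and 1 SD). With no shift after diagnosis there is no inflation.

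Two stronger readings are tempting. One is that the study will report established disease as prediction. The documents do not support this: it happens only if post-diagnosis values are used as predictors or in an undivided contrast that is then described as early, and predictors limited to 12 weeks would escape it in these scenarios. The other is that the extra visits are the sole cause. They enlarge the problem, but scheduled 28- and 36-week visits can also follow diagnosis, so dropping the extra visits would not cure it.

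**What to change.** 1. Reconcile section 3 with section 6.1 and Figure 1 on which women are offered extra phase-two visits.
2. In section 9.2, for any claim of early detection or prediction, state a prediction time, for example landmarks at the scheduled 12-, 28- and 36-week visits. Use only predictors measured at or before it, and exclude women already diagnosed or delivered by then.
3. Run the early-trajectory comparison on measurements made before diagnosis.
4. Analyse post-diagnosis visits separately, or with a time-varying diagnosis or treatment term, and report them as a description of established disease.
5. Keep the planned antihypertensive subgroup.
6. Record the date of diagnosis. Section 7 already collects pregnancy complications, and the Figure 1 visits already start at diagnosis.

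The cost is a few sentences and one data field; no measurement is discarded. The real downside is fewer late case measurements in the early-trajectory comparison and few cases left at the later landmarks, especially at 36 weeks if many diagnoses come before then. Estimates there will be imprecise and should be reported as such.
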